
Other hematologic DLTs per Section 5.5.2
	
 • Patients who have a dose-limiting hematological toxicity that does not resolve to meet eligibility or baseline parameters within 21 days after the planned start of the next treatment cycle must be removed from protocol therapy.

Non-Hematological Toxicity	Action
-----------------------------------	---------------

Non-hematological DLTs per Section 5.5.1
	
 • Patients who have any dose-limiting non-hematological toxicity (as defined in Section 5.5.1) may continue on protocol therapy upon meeting eligibility lab requirements or baseline but should receive subsequent doses at the next lower dose level of ABI-009. • If any non-hematological dose-limiting toxicity recurs after one dose reduction of ABI-009, the patient must be removed from protocol therapy. • Patients who have a dose-limiting non-hematological toxicity that does not resolve to baseline or eligibility within 21 days after the planned start of the next treatment cycle must be removed from protocol therapy.
---	---

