6.3 Dose Modification Guidelines for Cycle 2 or greater

Hematological Toxicity: Thrombocytopenia	Action
Platelets \geq 75,000/mm ³	
 • Continue protocol therapy.
Platelets < 75,000/mm ³	
 • ABI-009 as per Section 6.1 & Section 6.2. • Irinotecan & temozolomide will be continued at full dose.
Platelets < 50,000/mm ³	
 • ABI-009 as per Section 6.1 & Section 6.2. • Irinotecan & temozolomide will be continued at full dose.
Other thrombocytopenia DLTs per Section 5.5.2 on Day 8	
 • ABI-009 as per Section 6.1 & Section 6.2. • Irinotecan & temozolomide will be continued at full dose.

Hematological Toxicity: Neutropenia	Action
Grade 1-3	
 • Continue protocol therapy.
Grade 4	
 • ABI-009 as per Section 6.1 & Section 6.2. • Irinotecan & temozolomide will be continued at full dose.
Other neutropenia DLTs per Section 5.5.2 on Day 8	
 • ABI-009 as per Section 6.1 & Section 6.2. • Irinotecan & temozolomide will be continued at full dose.

Non-Hematological Toxicity	Action
Grade 1-2	
 Continue protocol therapy.
Grade 3-4	
 ABI-009 as per Section 6.1 & Section 6.2. Irinotecan & temozolomide will be continued at full dose.

Non-Hematological Toxicity	Action
Non-hematological DLTs per Section 5.5.1	
 ABI-009 as per Section 6.1 & Section 6.2. Irinotecan & temozolomide will be continued at full dose. Patients who experience dose-limiting non-hematological dose-limiting toxicity after one dose reduction (if starting at DL -1) or if the patient is being treated on the lowest dose level, protocol therapy should be discontinued. Patients who have a dose-limiting non-hematological toxicity that does not resolve to baseline or eligibility within 21 days after the planned start of the next treatment cycle must be removed from protocol therapy.

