6.4 Dose Modifications for Elevated Fasting Triglycerides

The following guidelines should be used for patients who develop elevated fasting triglycerides.

Continue irinotecan and temozolomide at full dose for cycles 2 or greater.

Grade	Action
Grade 2	
 Continue ABI-009; if triglycerides are between 301 and 400 mg/dL consider treatment with an HMG-CoA reductase inhibitor depending upon recommendations of institutional hyperlipidemia consultants. HMG-CoA reductase inhibitor is recommended if triglycerides are between 401 and 500 mg/dL
Grade 3-4	
 Hold ABI-009 until recovery to \leq Grade 2 An HMG-CoA reductase inhibitor should be started, and dosages should be adjusted based upon recommendations from institutional hyperlipidemia consultants Upon retreatment at the same dose level, if Grade 3 or 4 toxicity recurs, lipid lowering medication should be adjusted in consultation with institutional hyperlipidemia consultants. ABI-009 should be held until recovery to \leq Grade 2. Upon retreatment with ABI-009 concurrent with an HMG-CoA reductase inhibitor, if Grade 3 or 4 elevations recur, ABI-009 should be held until recovery to \leq Grade 2. Further lipid lowering

	medication options should be discussed with institutional hyperlipidemia consultants. Upon recovery to \leq Grade 2, ABI-009 should be restarted at the next lower dose level. If the patient is being treated on the lowest dose level, protocol therapy should be discontinued.
--	---

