6.5 Dose Modifications for Elevated Fasting Cholesterol

The following guidelines should be used for patients who develop elevated fasting cholesterol.

Continue irinotecan and temozolomide at full dose for cycles 2 or greater.

Grade	Action
Grade 2	
 Continue ABI-009; consider treatment with an HMG-CoA reductase inhibitor depending upon recommendations of institutional hyperlipidemia consultants.
Grade 3	
 An HMG-CoA reductase inhibitor should be started, and dosages adjusted based upon recommendations of institutional hyperlipidemia consultants. It is expected that optimal effects of the lipid lowering medication will be observed 2-4 weeks after its initiation. Treatment with ABI-009 is to be restarted at the same dose level when recovery of hypercholesterolemia to \leq Grade 2 is observed.
Grade 4	
 Hold ABI-009. An HMG-CoA reductase inhibitor should be started, and dosages should be adjusted based upon recommendations from institutional hyperlipidemia consultants. It is expected that optimal effect of the lipid lowering medication will be observed 2-4 weeks after initiation. ABI-009 is to be restarted at the same dose level when recovery to \leq Grade 2 cholesterol is observed. Upon retreatment with ABI-009 concurrent with an HMG-CoA reductase inhibitor, if Grade 4 elevations recur, ABI-009 should be held until recovery to \leq Grade 3. Further lipid lowering medication options should be discussed with institutional hyperlipidemia consultants. Upon recovery to \leq Grade 3 cholesterol, ABI-009 should be restarted at the next lower dose level. If the patient is being treated on the lowest dose level, protocol therapy should be discontinued.

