6.6 Dose Modifications for Hyperglycemia

The following guidelines should be used for patients who develop hyperglycemia based on fasting glucose levels.

Grade	Action
Grade 1-2	
 Continue ABI-009. Grade 2 may initiate oral antiglycemic agent*.
Grade 3	
 Initiate insulin therapy as indicated. Hold ABI-009 until fasting serum glucose is consistently \leq 250

	
mg/dL or ≤ 13.9 mmol.
 
 • Resume ABI-009 at same dose IF patient is asymptomatic, AND fasting serum glucose is consistently ≤ 250 mg/dL or ≤ 13.9 mmol) without glycosuria. The patient may continue to receive concomitant insulin or an oral diabetic agent for the management of hyperglycemia while receiving ABI-009. • If the fasting serum glucose value of $\geq 250 - 500$ mg/dL or $> 13.9 - 27.8$ mmol/L recurs and does not return to a fasting value ≤ 250 mg/dL or ≤ 13.9 mmol/L despite a stable dose of insulin and an oral diabetic agent Insulin and an oral diabetic agents should be tried before declaring a patient's hyperglycemia refractory to therapy. If the fasting serum glucose value of ≥ 250 mg/dL or > 13.9 mmol/L recurs and does not return to a fasting value ≤ 250 mg/dL or ≤ 13.9 mmol/L despite the use of insulin and an oral diabetic agent, subsequent doses of ABI-009 should be decreased to the next lower dose level. • If a patient experiences recurrence of a fasting serum glucose ≥ 250 mg/dL or > 13.9 mmol/L which does not return to ≤ 250 mg/dL or ≤ 13.9 mmol despite insulin, an oral diabetic agent AND the dose reduction, patient should be taken off protocol therapy. If the patient was already being treated at the lowest dose level, or if hyperglycemia > 250 mg/dL or > 13.9 mmol/L has recurred despite reduction of ABI-009 to the lowest dose level, the patient should be taken off protocol therapy.

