Grade 4	
 • Hold ABI-009 until resolution to fasting serum glucose is consistently ≤ 250 mg/dL or ≤ 13.9 mmol. • Resume ABI-009 with one dose level reduction IF patient is asymptomatic AND serum glucose is consistently consistently ≤ 250 mg/dL or ≤ 13.9 mmol without glycosuria. The patient may continue to receive concomitant insulin or an oral diabetic agent for the management of hyperglycemia while receiving ABI-009. • If Grade 4 hyperglycemia recurs and does not return to consistently ≤ 250 mg/dL or ≤ 13.9 mmol (despite a stable dose of insulin, an oral diabetic agent, and dose reduction to the next lower dose level, then subsequent doses of ABI-009 should be reduced again so that the new dose is two dose levels below the patient's starting dose. If the patient was already being treated at the lowest dose level, or if the fasting serum glucose is > 250 mg/dL or > 13.9 mmol has recurred despite reduction of ABI-009 to the lowest dose level, the patient should be taken off protocol therapy.

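### For a first-episode metabolic DLT, Sections 6.2/6.3 and Sections 6.4–6.6 give different ABI-009 doses and restart thresholds, and nothing says which prevails

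*Combined protocol and SAP*

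**What the plan says.** Section 5.5.1.1 makes any attributable non-hematological toxicity of Grade 3 or above a DLT, with listed exclusions. Grade 3–4 triglycerides and Grade 3–4 cholesterol are excluded only if they fall to Grade 2 or less before the next cycle. Grade 3 glucose is excluded only if the fasting value returns to 250 mg/dL or less by then. Grade 4 glucose has no exclusion.

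The non-hematological row of 6.2 is addressed to "Patients who have any dose-limiting non-hematological toxicity (as defined in Section 5.5.1"). They may continue once laboratory values meet eligibility or baseline, but "should receive subsequent doses at the next lower dose level of ABI-009". Failure to reach baseline or eligibility within 21 days of the next cycle's planned start means removal. On recurrence the row says: "If any non-hematological dose-limiting toxicity recurs after one dose reduction of ABI-009, the patient must be removed from protocol therapy".

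Section 6.3 applies 6.1 and 6.2 from Cycle 2. For non-hematological DLTs it adds that "if the patient is being treated on the lowest dose level, protocol therapy should be discontinued".

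The toxicity-specific sections read differently:

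- 6.4, triglycerides Grade 3–4: hold until Grade 2 or less, then "Upon retreatment at the same dose level, if Grade 3 or 4 toxicity recurs", adjust the lipid drug.
- 6.5, cholesterol Grade 4: "ABI-009 is to be restarted at the same dose level when recovery to" Grade 2 or less is seen. Grade 3 also restarts at the same level.
- 6.6, glucose Grade 3: "Resume ABI-009 at same dose IF patient is asymptomatic" and fasting glucose is consistently 250 mg/dL or less without glycosuria.
- 6.6, glucose Grade 4: resume one level lower. If it recurs and does not resolve, later doses "should be reduced again so that the new dose is two dose levels below" the starting dose, unless the lowest level has been reached, when the patient comes off therapy.

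**The concern.** An attributable metabolic event that misses the recovery deadline in 5.5.1.1 but recovers soon afterwards falls under both sets of rules. One lowers the dose, or stops therapy at the lowest level in Cycle 2+. The other returns the child to the dose that preceded the event. A site cannot follow both.

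This is a safety rule in a pediatric dose-finding trial. It also determines what is given in later cycles. A child with a metabolic DLT in Cycle 1 may or may not contribute Cycle 2 combination data at the assigned dose, which bears on the combination toxicity description (1.1.3), the Cycle 2 pharmacokinetics (1.1.4) and response (1.2.1).

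**Working it through.** No design figure of the plan bears on this point. The check sets the passages side by side.

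**1. First-episode events that meet the DLT definition**

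| Event | 6.2 / 6.3 | 6.4–6.6 | Agree? |
|---|---|---|---|
| Triglycerides Grade 3–4 | one level down | same level (6.4, implied) | No |
| Cholesterol Grade 3 | one level down | same level (6.5) | No |
| Cholesterol Grade 4 | one level down | same level (6.5) | No |
| Glucose Grade 3 | one level down | same level (6.6) | No |
| Glucose Grade 4 | one level down | one level down (6.6) | Yes |

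Four of five rows conflict, with at least one in each of 6.4, 6.5 and 6.6.

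**2. Search for a precedence rule.** The 6.2 row makes no exception for metabolic events. Section 6.3 refers back to 6.1 and 6.2, not forward to 6.4–6.6. Sections 6.4–6.6 are not limited to events that fall short of a DLT, and they do not mention 6.2 or 6.3. Section 5.2 lets a new cycle start if Section 6.0 permits it, without saying which part.

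**3. Dose consequence, using the levels in 5.3.1**

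| Level when the DLT occurs | 6.2 / 6.3 | 6.4–6.6 |
|---|---|---|
| DL -2, Cycle 2+ | discontinue (6.3) | 15 mg/m² |
| DL -2, Cycle 1 | a level below 15 mg/m², which does not exist; no lowest-level instruction in this row | 15 mg/m² |
| DL -1 | 15 mg/m² | 20 mg/m² |

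For DL -1 the difference is (20 − 15)/20 = 25%. That level is closed to new patients, so the figure is illustrative. The thrombocytopenia row of 6.2 does say what to do at the lowest level; the non-hematological row does not.

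**4. Restart threshold.** Eligibility (4.1.8.6) requires triglycerides and cholesterol of 300 mg/dL or less and glucose within the upper normal limit for age. Section 6.4 restarts at Grade 2 or less, and its own Grade 2 row runs to 500 mg/dL. A child whose triglycerides have fallen to 400 mg/dL may restart under 6.4. Under 6.2 the same child may not, because both eligibility and the baseline it implies are capped at 300. If the value is still 400 mg/dL 21 days after the planned start, 6.2 removes the child. Section 6.5 likewise restarts at Grade 2 or less, and 6.6 at 250 mg/dL or less.

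**5. Can the case arise?** Section 6.5 expects the lipid drug's best effect 2–4 weeks after it is started. Assume a start on Day 8, one of the weekly lipid checks in 8.1. Then 8 + 14 = Day 22 and 8 + 28 = Day 36. The next cycle is due on Day 22, and the 6.2 window closes at 22 + 21 = Day 43. Recovery between the two dates is foreseeable. Section 2.1.4 lists triglycerides among the DLTs of the earlier temsirolimus combination trial.

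**6. Recurrence after one reduction (6.2 removal against a second reduction in 6.6, Grade 4)**

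- Start at DL -2: already at the lowest level, so 6.6 also takes the patient off.
- Start at DL -1: 20 to 15 is the lowest level, so 6.6 also takes the patient off.
- Start at DL 1: 35 to 20 to 15 is possible under 6.6, while 6.2 removes at 20.

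Section 2.6 reports 5 patients at DL 1 and 13 at DL -1, and 5 + 13 = 18 is everyone enrolled by August 2019. At most five patients can therefore be in the conflicting case. The documents do not say whether any remain on therapy.

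**The case against.** The best defence is that the specific rule displaces the general one. Each of 6.4–6.6 opens by addressing patients who develop that abnormality, and 5.5.1.1 cites 6.6 in connection with managing glucose. A site might well read it so. But the protocol never says it, and 6.2 covers any such DLT. Where the authors wanted the same dose after a DLT, they wrote it into 6.2 itself, for neutropenia. The lipid citations in 5.5.1.1 concern the fasting retest only.

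A second defence is central oversight: suspected DLTs go to the Study Chair within 24 hours (5.4), dose modifications are notified (6.0), and the data are reviewed weekly (14.4.2). This makes divergent handling less likely, but it does not settle which rule the Study Chair should apply.

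A third is that the overlap is small. This stands. Events that recover in time are not DLTs, and for those 6.4–6.6 operate alone. Section 2.6 says that all DLTs so far were hematologic. If the next cycle in 5.5.1.1 means its actual, delayed start, fewer events become DLTs. The protocol does not define it, although 6.2 counts from the planned start.

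A reader might infer that every late-recovering metabolic event is affected. The text does not support that: first-episode Grade 4 glucose agrees, and the later recurrence steps in 6.4, in 6.5 for Grade 4 and in 6.6 already reduce the dose or stop therapy.

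**Conclusion.** The conflict is real and limited. It covers first-episode, attributable Grade 3–4 triglycerides, Grade 3–4 cholesterol and Grade 3 glucose that are unrecovered before the next cycle but recover within the 21-day window. For these, dose and restart threshold depend on the section read. At DL -2 the Cycle 2+ readings are discontinuation or 15 mg/m², and the Cycle 1 case has no workable instruction in 6.2.

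Three stronger readings should not be drawn. First, discontinuation at the lowest level for a non-hematological DLT is stated in 6.3, not in the 6.2 row. Second, the recurrence conflict does not reach patients who started at DL -1 or DL -2. Third, the tolerability decision at DL -2 is not in doubt: an event that is a DLT is counted whatever dose follows, and 11.2.1 replaces only patients without a DLT. What changes is later dosing, safety and the later-cycle data.

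The conclusion assumes that the recovery deadline in 5.5.1.1 is the planned start of the next cycle. The number of children affected cannot be estimated from the documents. This is a drafting inconsistency that should be corrected because it concerns a dosing and discontinuation rule.

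**What to change.** Reconcile the non-hematological rows of 6.2 and 6.3 with 6.4–6.6. State which section governs a metabolic toxicity that meets 5.5.1, and cover four items:

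- the dose after a first episode;
- the restart threshold;
- a Cycle 1 DLT in a patient already at the lowest level;
- recurrence after one reduction, for anyone who started at DL 1 or higher.

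In 5.5.1.1, say whether the deadline is the planned or the actual start of the next cycle. Record in the database which rule was applied to any patient with such an event, so that later-cycle data can be read against the dose given. Which clinical rule to adopt is for the study team.

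The cost is about one cross-reference sentence in each of 6.2 and 6.3 and a clarifying phrase in 5.5.1.1, within an amendment. No extra patients or procedures are needed.

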6.3 Dose Modification Guidelines for Cycle 2 or greater

Hematological Toxicity: Thrombocytopenia	Action
Platelets \geq 75,000/mm ³	
 • Continue protocol therapy.
Platelets < 75,000/mm ³	
 • ABI-009 as per Section 6.1 & Section 6.2. • Irinotecan & temozolomide will be continued at full dose.
Platelets < 50,000/mm ³	
 • ABI-009 as per Section 6.1 & Section 6.2. • Irinotecan & temozolomide will be continued at full dose.
Other thrombocytopenia DLTs per Section 5.5.2 on Day 8	
 • ABI-009 as per Section 6.1 & Section 6.2. • Irinotecan & temozolomide will be continued at full dose.

Hematological Toxicity: Neutropenia	Action
Grade 1-3	
 • Continue protocol therapy.
Grade 4	
 • ABI-009 as per Section 6.1 & Section 6.2. • Irinotecan & temozolomide will be continued at full dose.
Other neutropenia DLTs per Section 5.5.2 on Day 8	
 • ABI-009 as per Section 6.1 & Section 6.2. • Irinotecan & temozolomide will be continued at full dose.

Non-Hematological Toxicity	Action
Grade 1-2	
 Continue protocol therapy.
Grade 3-4	
 ABI-009 as per Section 6.1 & Section 6.2. Irinotecan & temozolomide will be continued at full dose.

Non-Hematological Toxicity	Action
Non-hematological DLTs per Section 5.5.1	
 ABI-009 as per Section 6.1 & Section 6.2. Irinotecan & temozolomide will be continued at full dose. Patients who experience dose-limiting non-hematological dose-limiting toxicity after one dose reduction (if starting at DL -1) or if the patient is being treated on the lowest dose level, protocol therapy should be discontinued. Patients who have a dose-limiting non-hematological toxicity that does not resolve to baseline or eligibility within 21 days after the planned start of the next treatment cycle must be removed from protocol therapy.

6.4 Dose Modifications for Elevated Fasting Triglycerides

The following guidelines should be used for patients who develop elevated fasting triglycerides.

Continue irinotecan and temozolomide at full dose for cycles 2 or greater.

Grade	Action
Grade 2	
 Continue ABI-009; if triglycerides are between 301 and 400 mg/dL consider treatment with an HMG-CoA reductase inhibitor depending upon recommendations of institutional hyperlipidemia consultants. HMG-CoA reductase inhibitor is recommended if triglycerides are between 401 and 500 mg/dL
Grade 3-4	
 Hold ABI-009 until recovery to \leq Grade 2 An HMG-CoA reductase inhibitor should be started, and dosages should be adjusted based upon recommendations from institutional hyperlipidemia consultants Upon retreatment at the same dose level, if Grade 3 or 4 toxicity recurs, lipid lowering medication should be adjusted in consultation with institutional hyperlipidemia consultants. ABI-009 should be held until recovery to \leq Grade 2. Upon retreatment with ABI-009 concurrent with an HMG-CoA reductase inhibitor, if Grade 3 or 4 elevations recur, ABI-009 should be held until recovery to \leq Grade 2. Further lipid lowering

	medication options should be discussed with institutional hyperlipidemia consultants. Upon recovery to \leq Grade 2, ABI-009 should be restarted at the next lower dose level. If the patient is being treated on the lowest dose level, protocol therapy should be discontinued.
--	---

6.5 Dose Modifications for Elevated Fasting Cholesterol

The following guidelines should be used for patients who develop elevated fasting cholesterol.

Continue irinotecan and temozolomide at full dose for cycles 2 or greater.

Grade	Action
Grade 2	
 Continue ABI-009; consider treatment with an HMG-CoA reductase inhibitor depending upon recommendations of institutional hyperlipidemia consultants.
Grade 3	
 An HMG-CoA reductase inhibitor should be started, and dosages adjusted based upon recommendations of institutional hyperlipidemia consultants. It is expected that optimal effects of the lipid lowering medication will be observed 2-4 weeks after its initiation. Treatment with ABI-009 is to be restarted at the same dose level when recovery of hypercholesterolemia to \leq Grade 2 is observed.
Grade 4	
 Hold ABI-009. An HMG-CoA reductase inhibitor should be started, and dosages should be adjusted based upon recommendations from institutional hyperlipidemia consultants. It is expected that optimal effect of the lipid lowering medication will be observed 2-4 weeks after initiation. ABI-009 is to be restarted at the same dose level when recovery to \leq Grade 2 cholesterol is observed. Upon retreatment with ABI-009 concurrent with an HMG-CoA reductase inhibitor, if Grade 4 elevations recur, ABI-009 should be held until recovery to \leq Grade 3. Further lipid lowering medication options should be discussed with institutional hyperlipidemia consultants. Upon recovery to \leq Grade 3 cholesterol, ABI-009 should be restarted at the next lower dose level. If the patient is being treated on the lowest dose level, protocol therapy should be discontinued.

6.6 Dose Modifications for Hyperglycemia

The following guidelines should be used for patients who develop hyperglycemia based on fasting glucose levels.

Grade	Action
Grade 1-2	
 Continue ABI-009. Grade 2 may initiate oral antiglycemic agent*.
Grade 3	
 Initiate insulin therapy as indicated. Hold ABI-009 until fasting serum glucose is consistently \leq 250

	
mg/dL or ≤ 13.9 mmol.
 
 • Resume ABI-009 at same dose IF patient is asymptomatic, AND fasting serum glucose is consistently ≤ 250 mg/dL or ≤ 13.9 mmol) without glycosuria. The patient may continue to receive concomitant insulin or an oral diabetic agent for the management of hyperglycemia while receiving ABI-009. • If the fasting serum glucose value of $\geq 250 - 500$ mg/dL or $> 13.9 - 27.8$ mmol/L recurs and does not return to a fasting value ≤ 250 mg/dL or ≤ 13.9 mmol/L despite a stable dose of insulin and an oral diabetic agent Insulin and an oral diabetic agents should be tried before declaring a patient's hyperglycemia refractory to therapy. If the fasting serum glucose value of ≥ 250 mg/dL or > 13.9 mmol/L recurs and does not return to a fasting value ≤ 250 mg/dL or ≤ 13.9 mmol/L despite the use of insulin and an oral diabetic agent, subsequent doses of ABI-009 should be decreased to the next lower dose level. • If a patient experiences recurrence of a fasting serum glucose ≥ 250 mg/dL or > 13.9 mmol/L which does not return to ≤ 250 mg/dL or ≤ 13.9 mmol despite insulin, an oral diabetic agent AND the dose reduction, patient should be taken off protocol therapy. If the patient was already being treated at the lowest dose level, or if hyperglycemia > 250 mg/dL or > 13.9 mmol/L has recurred despite reduction of ABI-009 to the lowest dose level, the patient should be taken off protocol therapy.
Grade 4	
 • Hold ABI-009 until resolution to fasting serum glucose is consistently ≤ 250 mg/dL or ≤ 13.9 mmol. • Resume ABI-009 with one dose level reduction IF patient is asymptomatic AND serum glucose is consistently consistently ≤ 250 mg/dL or ≤ 13.9 mmol without glycosuria. The patient may continue to receive concomitant insulin or an oral diabetic agent for the management of hyperglycemia while receiving ABI-009. • If Grade 4 hyperglycemia recurs and does not return to consistently ≤ 250 mg/dL or ≤ 13.9 mmol (despite a stable dose of insulin, an oral diabetic agent, and dose reduction to the next lower dose level, then subsequent doses of ABI-009 should be reduced again so that the new dose is two dose levels below the patient's starting dose. If the patient was already being treated at the lowest dose level, or if the fasting serum glucose is > 250 mg/dL or > 13.9 mmol has recurred despite reduction of ABI-009 to the lowest dose level, the patient should be taken off protocol therapy.

